## Brief synopsis of the proposed research

Current oral anti-coagulation for atrial fibrillation is most commonly performed with warfarin. Warfarin is a vitamin K antagonist that has been shown in non-randomized trials to increase vascular calcification. Increased vascular calcification has been tied to increased cardiovascular events (CVE). This study will randomize patients currently taking warfarin to either continue on warfarin or be switched to rivaroxaban. Rivaroxaban is an oral anti-coagulant that works by inhibiting Factor Xa, and has no interaction with vitamin K. This study is a randomized, open label study that will randomize 120 patients and have them undergo blood tests and a calcium scan at baseline, and again after 12 months. Patients will be seen quarterly for examinations, safety checks and supply of rivaroxaban, as well as follow up INR testing for warfarin.

### **1. Introduction:**

Vitamin K-antagonists (VKA) are the most widely used anti-thrombotic drugs with substantial efficacy in reducing risk of arterial and venous thrombosis. Several lines of evidence indicate, however, that VKA inhibit not only post-translational activation of vitamin K-dependent coagulation factors but also synthesis of functional extra-hepatic vitamin K-dependent proteins thereby eliciting undesired side-effects. Vascular calcification is one of the recently revealed side-effects of VKA. Vascular calcification is an actively regulated process involving vascular cells and a number of vitamin K-dependent proteins.

### **2. Background Information**

*Coronary artery calcium (CAC) is strongly associated with atherosclerotic burden and predicts coronary heart disease (CHD) events and mortality. Progression of CAC has also been shown to independently be associated with increased CVD events and all-cause mortality. Warfarin has recently been shown to not only increase calcification, but markers of atherosclerotic plaque in both animals and humans.*

Rivaroxaban has been shown to reduce the risk of stroke significantly and to be non-inferior to warfarin. However, the rate of myocardial infarction was 9% lower in the rivaroxaban group than in the warfarin group in the Rocket AF study, and similarly the myocardial infarction rate was 12% lower in the apixaban group in the Aristotle study, but the difference was not significant in either trial. The potential of long term benefit by avoiding VKA therapy may be much greater for a CV event reduction. The study proposed will evaluate markers of CAC progression and atherosclerosis development, including adverse plaque characteristics such as positive remodeling and stenosis severity, which have long term outcome data supporting that slowing these processes will be associated with lower CV events.

### CAC and Progression

Multiple studies have been done to demonstrate the feasibility of measuring CAC change at 12 months. Initial studies suggested that treatment with statins was associated with slower progression of CAC. Callister et al.i studied 149 patients. Patients underwent a baseline and follow-up EBT scan at 12 months and serial LDL cholesterol measurements were obtained.

Progression of calcium volume score was seen in all untreated patients (n = 44; mean LDL 147 ± 22 mg/dl) and averaged 52 ± 36% per year. In contrast, the mean yearly calcium volume score change for all treated patients (n = 105; mean LDL 114 ± 23 mg/dl) was 5 ± 28% (p < 0.001 vs. untreated patients). Among the treated patients, 65 individuals attained a LDL level <120 mg/dl (mean LDL 100 ± 17 mg/dl) and showed a net regression of their calcium volume score (-7 ± 22%). In patients who received HMG-CoA reductase inhibitors but maintained an average LDL >120 mg/dl (mean LDL 139 ± 18 mg/dl), the mean yearly calcium volume score progression was 25 ± 22%. Similar one year studies by [name] et al.,ii and Achenbach et al.,iii showed that statin therapy is associated with slowing of progression of coronary calcium.

The BELLES trialiv was a prospective randomized study of 615 postmenopausal and dyslipidemic women randomized after initial CAC scan to atorvastatin 80 mg/day or pravastatin 40 mg/day. A second scan was repeated in 12 months. The attained mean LDL cholesterol level was significantly lower with atorvastatin (94 mg/dl) than pravastatin (129 mg/dl). Nonetheless, the median relative change in the calcium volume score was not different between the two treatment arms (15.1% and 14.3% for atorvastatin and pravastatin, respectively, p = NS).

Another large scale clinical trial using CAC at one year intervals was the Treat-to-Goal Study—a randomized, multicenter clinical trial—comparing the calcium-free, non-absorbable polymer sevelamer to traditional calcium-based phosphate binders.v Study endpoints included serum levels of phosphorus, calcium, intact parathyroid hormone (PTH), and lipids, as well as change in calcification of the coronary arteries and thoracic aorta quantified by CT. Two hundred adult hemodialysis patients, who had received hemodialysis for a median of 3 years prior to study entry, were randomized in 15 medical centers in Europe and the United States. During the study period, phosphate binders were adjusted to maintain serum phosphorus levels between 3.0 and 5.0 mg/dL, serum calcium levels between 8.5 and 10.5 mg/dL, and serum PTH levels between 150 to 300 pg/mL. EBT was performed at the start of the study, and after 6 and 12 months of treatment. In spite of a similar control of serum phosphorus and calcium, coronary and aortic calcification progressed significantly in the calcium-treated patients while there was no statistically significant change from baseline in the sevelamer group. At one year follow-up, the median relative change in coronary and aorta scores were 25% and 28% and 6% and 5% in the calcium and sevelamer group, respectively (p = 0.02 for all intergroup comparisons).

One recent study by Fitch et alvi evaluated a 12 month, randomized, placebo controlled trial to investigate lifestyle modification (LSM) and metformin, alone and in combination was conducted among HIVinfected patients with metabolic syndrome. The primary endpoint was change in CAC score. Fasting lipids, insulin and measures of cardiorespiratory fitness were assessed. 50 subjects (age 47 ± 1 yr) were randomized, 76% were male, 48% White, 30% African American, and 18% Hispanic. Metformin-treated subjects demonstrated significantly less progression of CAC over 12 months (-1 ± 2 vs. 33 ± 17, P=0.004), less progression in calcified plaque volume (-0.4 ± 1.9 vs. 27.6 ± 13.8 mm^3, P=0.008), improved HOMA-IR (-0.1 ± 0.4 vs. 1.1 ± 0.4, P=0.05) and RANKL/OPG ratio (-0.0002 ± 0.0002 vs. 0.0003 ± 0.0002, P=0.02) compared to placebo. Subjects randomized to LSM vs. no LSM showed significant improvement in HDL (3 ± 1 vs. -1 ± 1 mg/dl, P=0.03), and CRP (-1.57 ± 0.70 vs. 0.08 ± 0.45

mg/L, P=0.05). For CAC, the net effect of metformin (vs. placebo) controlling for LSM randomization was -42 and the net effect of LSM (vs. no LSM) controlling for metformin randomization was -24.

Three randomized 1 year studies were performed by [name]'s group, evaluating change in CAC over 12 months in relatively small cohorts under the influence of different formulations of Aged Garlic Extract (AGE). [name] et al. (2004)vii showed that in 23 patients with known coronary artery disease (CAD) or high risk patients (Framingham Risk > 20% over 10 years), over one year, AGE reduced the progression of CAC compared to placebo (7.5 +/- 9.4% versus 22.2 +/- 18.5%, respectively). Similarly, [name] et al. (2009)viii showed significant results in 65 intermediate risk patients (age 60 +/- 9 years) with Framingham risk of 10 – 20 % and baseline CAC > 30. In this study, AGE was administered with vitamin B12, folic acid, vitamin B6 and L-arginine. In one year follow-up the CAC progression was significantly lower in the treatment group versus placebo (6.8% versus 26.5%, p = 0.005). Lastly, Zeb et al. (2012)ix enrolled 65 asymptomatic intermediate risk (as defined by baseline CAC > 10) males, aged 55 +/- 6 years, and treated them with AGE plus co-enzyme Q10 (CoQ10) versus placebo. At 1 year, mean CAC progression was significantly lower in treatment group versus placebo (32 +/- 6 versus 58 +/- 8, p = 0.01).

## CAC and Events

*Coronary artery calcium (CAC) is strongly associated with atherosclerotic burden and predicts coronary heart disease (CHD) events and mortality (1-4). CAC scanning has been proposed as a measure to track CHD progression and the effects of risk factor modification on atherosclerosis (5-6). Multiple studies suggests that CAC progression is associated with CHD events (7-8). Recently, follow-up based on a large registry of subjects receiving serial CT scans showed progression of CAC to be strongly associated with total mortality (9). We have previously demonstrated in a prospective evaluation of 4,609 patients that, after adjusting for baseline score, age, sex, and time between scans, CAC progression (mean progression was 247 in this group) was associated with a 3.34 fold risk of all-cause mortality (HR 3.34; 95% CI: 2.65 to 4.21; p < 0.0001). The MESA study also demonstrated that CAC progression was strongly associated with increased CV events(10), following 5682 persons over 7.6 years. Among participants with baseline CAC, those with annual progression of  $\geq 300$  units had adjusted HR's of 3.8 (1.5-9.6) for total and 6.3 (1.9-21.5) for hard CHD compared to those without progression.*

## Warfarin and CAC Progression.

Vitamin K-antagonists (VKA) are the most widely used anti-thrombotic drugs with substantial efficacy in reducing risk of arterial and venous thrombosis. Several lines of evidence indicate, however, that VKA inhibit not only post-translational activation of vitamin K-dependent coagulation factors but also synthesis of functional extra-hepatic vitamin K-dependent proteins thereby eliciting undesired side-effects. Vascular calcification is one of the recently revealed

side-effects of VKA. Vascular calcification is an actively regulated process involving vascular cells and a number of vitamin K-dependent proteins. In experimental animal models as well as humans, VKA have been shown to promote medial elastocalcinosis. Mechanistic understanding of vascular calcification is essential to improve VKA-based treatments of both thrombotic disorders and atherosclerosis.

Vascular calcification is a marker of increased cardiovascular morbidity and mortality.(11) Matrix Gla protein (MGP) is an important inhibitor of calcification.(12-15) In animal studies, where carboxylation of MGP was blocked by vitamin K antagonists, excessive calcifications of the arteries were found.(16) In humans, calcification of the coronary arteries (CAC) and heart valves is increased in patients on vitamin K antagonists, whereas intake of vitamin K is associated with less progression of CaC.(17-20) VKA use has been associated with increased vascular calcification, which may impart long term risk. Several studies have demonstrated the contribution of VKA use to coronary artery calcification progression in AF patients. Rennenberg et al (21) selected 19 patients younger than 55 years who had no other cardiovascular risk factors and who had used coumarins for more than 10 years, and compared these to 18 matched healthy controls. The odds ratio for calcification in patients versus controls was 8.5 (95% confidence interval [CI] 2.01-35.95). Coumarin use and MGP were associated with calcification, even after adjusting for other risk factors. They concluded that long-term use of coumarins is associated with enhanced extracoronary vascular calcification, possibly through the inhibition of MGP carboxylation.

A prospective study using coronary calcium scans (22) was performed in 157 AF patients without significant cardiovascular disease (108 males; mean age  $57 \pm 9$  years). The duration of VKA treatment varied between 6 and 143 months (mean 46 months). No significant differences in clinical characteristics were found between patients on VKA treatment and non-anticoagulated patients. However, median coronary artery calcium scores differed significantly between patients without and patients with VKA treatment [0, inter-quartile range (IQR) 0-40, vs. 29, IQR 0-184;  $P = 0.001$ ]. Mean coronary calcium scores increased with the duration of VKA use (no VKA:  $53 \pm 115$ , 6-60 months on VKA:  $90 \pm 167$ , and  $>60$  months on VKA:  $236 \pm 278$ ;  $P < 0.001$ ). Multivariable logistic regression analysis revealed that age and VKA treatment were significantly related to increased coronary calcium score. Age and VKA treatment were independently related to increased coronary calcium score.

As vascular calcification is considered an independent risk factor for plaque instability, Schurgers (23) investigated the effect of VKA on coronary calcification in patients and on calcification of atherosclerotic plaques in the ApoE(-/-) model of atherosclerosis. A total of 266 patients (133 VKA users and 133 gender and Framingham Risk Score matched non-VKA users) underwent 64-slice MDCT to assess the degree of coronary artery disease (CAD). VKA-users developed significantly more calcified coronary plaques as compared to non-VKA users. ApoE(-/-) mice (10 weeks) received a Western type diet (WTD) for 12 weeks, after which mice were fed a WTD supplemented with vitamin K(1) (VK(1), 1.5 mg/g) or vitamin K(1) and warfarin (VK(1)&W; 1.5 mg/g & 3.0 mg/g) for 1 or 4 weeks, after which mice were sacrificed. Warfarin significantly increased frequency and extent of vascular calcification. Also, plaque calcification comprised microcalcification of the intimal layer. Furthermore, warfarin treatment decreased

plaque expression of calcification regulatory protein carboxylated matrix Gla-protein, increased apoptosis and, surprisingly outward plaque remodeling.

In this study, VKA use was associated with coronary artery plaque calcification in patients with suspected CAD and causes changes in plaque morphology with features of plaque vulnerability in ApoE(-/-) mice. These findings underscore the need for alternative anticoagulants that do not interfere with the vitamin K cycle.

#### Rate of Progression of CAC

Almost all randomized studies of coronary artery calcification progression were 1 year duration. Annualized studies have been performed with statins, ACE inhibitors, calcium channel blockers, garlic therapy, phosphate binders among others, all studies with 1 year duration.

#### Relationship of Coronary Artery Calcium and Unstable Plaque

The exact contribution of coronary artery calcification to the stability of atherosclerotic plaques is not clearly defined. Some studies describe that plaque calcification initially destabilizes a plaque by providing areas of interface between high- and low density where a plaque is more prone to rupture. Plaques may also rupture because of physical stress exerted by calcified nodules. However, calcification may also represent beneficial scaffolding which could be seen as protective by strengthening atherosclerotic plaque prone to rupture. But still then enhancing the process of calcification by VKA may promote vasomotor dysfunction in the coronary arterial tree.

[figure not shown]
#### Rivaroxaban

Rivaroxaban is a novel oral direct factor Xa inhibitor that has been shown to reduce the risk of stroke in a similar population in comparison with warfarin. The rate of myocardial infarction was 9% lower in the rivaroxaban group than in the warfarin group in the Rocket AF study and similarly the myocardial infarction rate was 12% lower in the apixaban group in Aristotle, but the difference was not significant in either trial. The potential of long term benefit by avoiding VKA therapy may be much greater for a CV event reduction. The study proposed will evaluate markers of CAC progression and atherosclerosis development, which have long term outcome data supporting that slowing these processes will be associated with lower CV events.

#### *CCTA*

C- Coronary Plaque Volume/Composition via Computed Tomography Angiography: (0 and 52 weeks)

Coronary plaque volume/composition will be measured using multi-detector computed tomography. Recent studies demonstrated the computed tomography angiography can accurately measure plaque characteristics including volume and composition with high reproducibility. Furthermore, they provide evidence that CT angiography is feasible and diagnostic utilizing radiation doses as low as 2 mSv without compromise of image quality, potentially removing one of the biggest barriers to more widespread implementation of cardiac CT and empowers serial coronary plaque volume assessment with CT angiography (figure 1).

Multislice computed tomography is a non-invasive technique that can easily detect CAD at its earliest stages reflected by the presence and severity of coronary artery calcification. Minor lesions in the main coronary arteries could be a sign of advanced vascular disease in the microvasculature which may lead to important ischaemia, possibly even influencing the AF substrate. A recent meta-analysis among 30 prospective studies revealed that the presence of calcifications is associated with a three- to four-fold higher risk for mortality and cardiovascular events.

CCTA is a novel non-invasive imaging test with high diagnostic performance for detection and quantification of anatomic stenosis compared to invasive coronary angiography (ICA) and intravascular ultrasound (IVUS). Beyond stenosis severity, CCTA also permits anatomic quantification of numerous other atherosclerotic plaque characteristics (APCs) (28, 29). These APCs include additional measures of stenosis severity (% diameter stenosis, % area stenosis, minimum luminal diameter [MLD], minimum luminal area [MLA]), plaque composition (non-calcified, calcified, “mixed”; lowest attenuation density; “spotty” calcification); plaque remodeling (positive, negative, intermediate), plaque burden (volume); and plaque location (proximal versus distal; relation to bifurcation). APCs have been described—both by intravascular methods and in studies with CCTA—to exhibit clinical import for plaque stability; and permit discrimination of patients experiencing stable angina versus acute coronary syndromes. We have performed and reported investigations demonstrating the unique value of plaque composition, low attenuation plaque, and coronary arterial remodeling for the identification of patients that exhibit myocardial ischemia and adverse cardiovascular outcome.

Further, we have published several papers related to the diagnostic performance of CCTA for volumetric quantification of coronary artery plaque volume, composition and other APCs; as well as has determined the utility of automated computational-based methods for coronary artery plaque characterization and quantification (30,32). To determine reliability of CT APC evaluation, we identified a high diagnostic accuracy of measured plaque volume by CCTA versus IVUS in 36 patients. In a separate study of 30 patients who underwent 2 CT scans within 200 days the number of plaques, and measured total, calcified plaque (CP) and non-calcified plaque (NCP) volume. Intra-, inter-, and inter-scan agreement for segments with no plaque was 100%. Intraobserver-interscan correlations of total, CP, and NCP volumes ( $r=0.93-0.97$ ,  $p<0.001$  for all), as well as interobserver-interscan correlations were also very good ( $r=0.81-0.96$ ,  $P$  values  $<0.001$ ).

To enhance CT APC evaluation efficiency, reliability and accuracy, our team has developed the first automated computer software algorithm (AutoPlaq) validated against IVUS that enables

accurate and rapid quantification of NCP and CP from CT. In 20 patients undergoing CT and IVUS, the software demonstrated excellent correlation to IVUS for NCP ( $r=0.94$ ,  $p<0.001$ ) and expert core lab measures for plaque volume ( $r=0.92$ ,  $p<0.001$ ), with no significant mean differences. Importantly, diagnostic time for the automated method was <10% of manual measurements. Reliability of the automated method was high compared to expert readers for CP and NCP volumes ( $R=0.88$  and  $0.94$ ,  $p<0.001$  for both) and plaque composition ( $R=0.90$ ,  $p<0.0001$ ). Our results are in keeping with a recent meta-analysis demonstrating high correlation of CT versus IVUS for cross-sectional area, plaque area, area stenosis, and volume. We have further corroborated these findings—and have demonstrated the robustness of CCTA (both by manual as well as automated methods—for the volumetric quantification of coronary atherosclerosis and arterial wall features.

To date, however, the longitudinal changes of coronary artery and plaque characteristics—particularly as they relate to warfarin use—has not been examined. This proposal encourages a comprehensive approach to identifying all aspects of coronary atherosclerosis progression related to medications that are vital to prevent strokes in persons with afib. These CT measures are active in the coronary artery disease pathway, providing quantitative measures of not only luminal stenosis severity, but plaque volume, plaque composition, plaque distribution, plaque length, and arterial remodeling. This proposal will significantly extend prior studies performed by our laboratory and others by examining the nature of coronary atherosclerosis progression, regression and stabilization under the influence of two different therapies. The feasibility and practicability of this study is rooted in the longstanding collaboration of investigators with unparalleled expertise, as well as the numerous preliminary studies performed at the investigators' institution.

### **Study Rationale**

The OVERALL HYPOTHESIS of this study is that use of rivaroxaban will slow progression of vascular calcification and coronary atherosclerosis as compared to warfarin therapy in patients with AFIB.

### **Study Objectives**

*Objective 1:* To demonstrate if treatment with rivaroxaban therapy, as compared to warfarin therapy, will slow the progression of calcified plaque, based upon the CAC score.

*Objective 2:* To evaluate if treatment with rivaroxaban therapy, as compared to warfarin therapy, will modify the progression, regression and stabilization of coronary atherosclerosis. Modifications will include differences in plaque volume, composition and arterial remodeling; as well as new atherosclerosis formation.

## **3. ETHICAL CONSIDERATIONS**

The Investigator will follow all appropriate requirements, including Good Clinical Practice (GCP), International Conference on Harmonization (ICH), Code of Federal Regulations (CFR). The study will be conducted by qualified personnel and be approved by the local. IRB/IEC.

#### **4. INVESTIGATIONAL PLAN AND STUDY DESIGN**

We propose a randomized, open label trial, to compare Rivaroxaban 20 mg oral once daily with food to warfarin (target international normalized ratio, 2.0 to 3.0) in patients with non-valvular atrial fibrillation. The primary endpoint will be CAC progression and key secondary objectives will be progression of total plaque, and development of new vulnerable plaques. Patients will be educated to maintain a low cholesterol diet through education to patients as well as medication compliance.

##### Study Design:

- a. Design. The study will be a single-center, randomized, open label comparison of Rivaroxaban **20 mg once daily with food** compared to warfarin therapy (INR target 2-3) for 52 weeks on coronary calcium, coronary plaque composition and volume. One hundred ten eligible subjects will be enrolled using a 1:1 ratio. The sample size in this study is based on exploratory considerations.
- b. Randomization and Stratification. Subjects who meet the eligibility criteria will be randomly assigned to receive rivaroxaban or warfarin
- c. **Endpoint Measures**

Primary - Rate of change in coronary calcium

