##### 2. Secondary Endpoints

1. To assess incident plaque rates and quantitative changes in different plaque types in patients randomized to warfarin vs. rivaroxaban using CTA, 12 months after an initial evaluation.
2. Evaluation of plaque progression rates and incident plaque rates in subjects treated with warfarin vs. rivaroxaban. In that context, we will:
  - a. determine whether subjects treated with rivaroxaban display slower rates of progression compared to warfarin treated subjects, after control for all CV risk factors and demographics

[figure not shown]
The study design calls for the enrollment of 120 eligible subjects of diverse ethnic population. Given dropout rate, at least 100 patients should be available for final analysis at the conclusion of 52 week follow-up. Baseline examination will include the results of their demographic, coronary risk factor, lab tests, coronary calcium, as well as coronary plaque volume/composition. All participants will be educated on a low-cholesterol diet at entry to the study. Baseline information regarding risk factors for atherosclerotic cardiovascular disease (cigarette smoking status, systemic hypertension, family history of premature atherosclerosis, menopausal and hormone replacement status in women, sedentary lifestyle, current medications, chest pain questionnaire and measures of obesity) will be determined. After randomization, participants will return quarterly (3, 6, 9 and 12 months to assess compliance with medication, and receive an additional supply of medicine. At 52 weeks follow up, coronary calcium and coronary plaque volume/composition will be measured by readers blinded to the randomization and clinical activities, who are not aware of study-group assignments

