## **13. STATISTICAL CONSIDERATIONS**

### Statistical analysis

All analyses will be performed on a full analysis set basis (those who stay in the trial to the follow up scan). For the primary analysis, ITT (defined as all those randomized into the study) will be used. Continuous variables will be expressed as mean and standard deviation; categorical variables expressed as absolute numbers and percentages. Baseline variables will be compared with an independent t-test (two tailed) after performing Levene's test for equality of variances in all normally distributed continuous variables and the Mann-Whitney test (two-tailed) in all not normally distributed variables. Categorical variables will be tested with two-sided Fisher's exact test. An analysis of variance (ANOVA) model with treatment as the main effect will be used to compare the treatment effect of rivaroxaban and warfarin treatment

strategies. For all measures, the analysis of covariance (ANCOVA) model controlling for baseline demographics and baseline CACS values will be performed. Treatment groups also will be compared with respect to incidence rates of adverse events, laboratory abnormalities, bleeding rates, and concomitant medication use. Measurements and change from baseline in coronary artery calcium scores, vital signs (blood pressure and pulse rate), continuous laboratory variables and compliance values will be summarized using descriptive statistics (mean, standard deviation, minimum, median and maximum) by treatment groups and visit. If the interaction of treatment by baseline laboratory values or CACS is significant at the 0.10 level or below, the nature of the interaction will be further explored. Spearman's rank correlation coefficient will be used for testing correlation between the mean Agatston score. All parameters showing a significant univariate relation with an increased coronary Agatston score and those representing a plausible mechanism in terms of calcification [age, VKA duration, left atrium (LA) diameter, statins, angiotensin-converting enzyme (ACE)-inhibitors] will be included as covariates in a logistic regression model (retention level set at 0.1), odds ratios and 95% confidence intervals (CIs) calculated, and results checked for interaction.

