### Sample Size

**Sample Size Estimation.** Sample sizes for each efficacy area have been calculated assuming performance of two-sided 0.05 level tests and 90% power for the primary endpoint and >85% power for the secondary endpoint to detect differences considered clinically meaningful and plausible based on prior studies. We have based sample sizes on at least 90% power in all end points because false negatives could lead to abandoning further study of a treatment that could have a major positive impact on myocardial infarction in this population. The primary endpoint is progression of atherosclerosis after 1 year of treatment with warfarin compared to rivaroxaban as measured by the annualized relative change in the coronary calcium score, as assessed by the Agatston score. The primary endpoint will be the percentage change in CAC from the baseline, which was calculated as follows:  $(CAC \text{ score at 1 year} - CAC \text{ score at baseline}) / CAC \text{ score at baseline} \times 100$ . From multiple 1 year randomized studies in [name] lab, the mean annualized relative change in the Agatston calcium score was  $27.2 \pm 9.5\%$  and on pilot-treatment group, we observed an average change of  $7.5 \pm 4\%$ . Given a 19.7 % annual change difference (27.2% vs. 7.5%) between two groups was observed from primary data, the trial requires 100 in total (50 patients per arm) to attain power of 90% to detect the effect size according to a two-tailed two-sample t-test at a significance level 0.05 (see figure). If we consider the secondary

endpoint (noncalcified plaque volume change), we will have >85% power without drop-off at a two-tailed significance level 0.05 with 120 subjects.

The secondary endpoint is noncalcified plaque volume, using cardiac CTA. Cardiac CTA has been used successfully by [name] to measure progression of atherosclerosis (30-32). In one relevant study, the mean annualized relative change in the non-calcified plaque volume among 62 subjects given statin was -0.037 with a standard deviation of 0.351. This secondary comparison has power of 0.80 to detect an effect size of 0.5, the mean difference in the annualized relative change in the non-calcified plaque volume between the rivaroxaban and warfarin, according to a two sample t-test at a two-tailed significance level 0.05.

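### Enrolment is given as 110 in one place and 120 in three others; at 110 the loss allowance behind the target of 100 evaluable patients is halved

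*Combined protocol and SAP*

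**What the plan says.** Four places in the combined protocol and SAP give or use a total.

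- Study Design, item (a): "One hundred ten eligible subjects will be enrolled using a 1:1 ratio".
- Brief synopsis: the study "will randomize 120 patients and have them undergo blood tests and a calcium scan at baseline".
- Enrolment narrative following the list of secondary endpoints: "The study design calls for the enrollment of 120 eligible subjects of diverse ethnic population". It continues: "Given dropout rate, at least 100 patients should be available for final analysis".
- Section 13, Sample Size: for the primary endpoint, "the trial requires 100 in total (50 patients per arm) to attain power of 90" per cent; for the secondary endpoint, "we will have >85% power without drop-off at a two-tailed significance level 0.05 with 120 subjects".

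The narrative refers to dropout but puts no number on it.

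**The concern.** The enrolment total tells a single-centre site when to stop recruiting, and the current text gives two. Item (a) is the formal design statement and carries the allocation ratio, so a reader could reasonably stop at 110. The rest of the plan is built on 120: that total is what leaves room for losses above the target of 100, and it is the total for which secondary power is quoted.

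Two things are at stake. The margin for patients who do not return for the 52-week scan is 10 at 110 and 20 at 120. And the secondary power statement, made for 120 patients with no losses, would not describe a trial of 110. Because no dropout rate is given, a reader cannot check whether either total is adequate.

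**Working it through.** **Can the two totals be reconciled?** Item (a) and the narrative both describe eligible subjects who are enrolled, so a screened-versus-randomised distinction does not help. The evaluable number is stated separately as at least 100, so 110 is not the evaluable number either. A figure near the narrative and one cited in the Sample Size section are not available, so this check covers the visible text only.

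**Loss that still leaves 100.** Maximum loss = 1 − 100/N.

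- N = 110: 1 − 100/110 = 9.1%, or 10 patients. The eleventh loss (10.0%) leaves 99.
- N = 120: 1 − 100/120 = 16.7%, or 20 patients.

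The plan states no rate, so the range below is assumed. Evaluable = N × (1 − loss), rounded down. Enrolment needed = 100/(1 − loss), rounded up.

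| Assumed loss | Evaluable from 110 | Evaluable from 120 | Enrolment needed for 100 |
|---|---|---|---|
| 5% | 104 | 114 | 106 |
| 10% | 99 | 108 | 112 |
| 15% | 93 | 102 | 118 |
| 20% | 88 | 96 | 125 |

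**Primary endpoint.** Inputs from Sample Size: means 27.2% and 7.5%, difference 19.7, printed spreads 9.5 and 4, two-sided 0.05, 90% power. The spreads carry no label and are read here as SDs.

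- The plan's own figure is 50 per arm. Pooled SD = √((9.5² + 4²)/2) = 7.29, so d = 19.7/7.29 = 2.70. By the normal approximation, n per arm = 2 × (1.960 + 1.282)² / 2.70² = 2.9, or 3 per arm. With SD 9.5 in both arms it is 5 per arm. The figure of 50 does not reproduce; that is a separate matter, and this point does not depend on it.
- At 55 per arm (110) and 60 per arm (120), power is essentially 100%.

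**Secondary endpoint.** Sample Size cites an effect size of 0.5, describes it as a mean difference in annualized relative change, and gives an SD of 0.351 from one earlier study. Two-sample t-test, two-sided 0.05, no losses:

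- If 0.5 is standardised: 73.8% at 55 per arm and 77.5% at 60 per arm, a gap of 3.7 points.
- If 0.5 is a raw difference: d = 0.5/0.351 = 1.42, and power exceeds 99.99% at both sizes.

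One further calculation bears on which total was meant. A one-sided 0.05 test at d = 0.5 gives 79.9% at 50 per arm and 85.9% at 60 per arm, close to the 0.80 and >85% in the text. The plan specifies two-tailed tests, so this is only a hint, but it points to 120 enrolled and 100 evaluable as the working numbers.

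**The case against.** The strongest reply is that this is probably one uncorrected number: the synopsis, the narrative and the Sample Size section agree on 120, and no stated dropout rate shows that 110 would fall short. That stands. It limits the size of the point but does not remove the contradiction.

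A second reply concerns the analysis set. The Statistical analysis section says "All analyses will be performed on a full analysis set basis (those who stay in the trial to the follow up scan", which suggests that each loss shrinks the analysed sample. The next sentence, however, assigns ITT, meaning everyone randomised, to the primary analysis, and the following paragraph applies ITT to the primary and secondary efficacy analyses. So the full-analysis-set sentence cannot carry the argument. The point rests on the narrative's own target of at least 100 for final analysis.

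A third reply is that item (a) also says "The sample size in this study is based on exploratory considerations", so precision about the total is not to be expected. That may excuse a loosely justified size, but it does not explain two different sizes. Conversely, a reader might infer that this sentence contradicts the power calculation in Section 13. The documents do not support that: the conclusions describe a pilot study, and an exploratory rationale can sit beside a power calculation.

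A reader might also infer that stopping at 110 would underpower the primary comparison. The printed means and SDs do not show this. Making 100 patients just enough would need a much larger SD than the Sample Size section gives.

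**Conclusion.** The contradiction is real and should be corrected before the plan is relied on. Its demonstrated size is a loss allowance of 10 patients (9.1%) instead of 20 (16.7%) against the stated target of 100, together with a secondary power statement that belongs to 120 and not to 110.

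It does not follow that the target would be missed; that depends on a loss rate the documents do not give. Nor is a loss of power established. Primary power is essentially 100% at either total, provided the printed spreads are SDs. For the secondary endpoint, the 3.7-point difference holds only if the effect size is standardised, and it vanishes on the raw reading. The consequence is therefore modest, and the case for acting is that the enrolment total is a basic operating figure and the correction is nearly free.

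**What to change.** 1. In Study Design, item (a), change *One hundred ten* to *One hundred twenty*, to match the synopsis, the enrolment narrative and the Sample Size section. If the sponsor does intend 110, those three places must change instead, and secondary power must be restated for 110.
2. In the enrolment narrative, replace the unquantified reference to dropout with the assumed percentage of patients without an evaluable 52-week scan. Give its source, for example the loss to repeat scanning in the earlier one-year calcium studies that the plan cites. Do not derive it backwards from 120.
3. Confirm that 120 × (1 − rate) is at least 100, which holds for rates up to 16.7%. If it does not hold, restate the evaluable target.

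The cost is one number and one sourced percentage, with no patients beyond the 120 already planned and no change to procedures.
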